## 5.2.2.1 Monoclonal Antibody IL-2 Receptor Blocker

All subjects will receive one of the following monoclonal antibody IL-2 receptor blockers: daclizumab or basiliximab

# 5.2.2.1.1 Daclizumab (Zenapax®)

Daclizumab (Zenapax®) is a humanized anti-CD25 monoclonal antibody in clinical use since 1997 for prophylaxis against acute organ rejection in subjects receiving a kidney allograft. Please refer to applicable product labeling and the Package Insert for its known and potential risks to human subjects.

Five I.V. doses of daclizumab will be given with all subsequent islet transplants. The first dose will be 2 mg/kg and will be given within two hours prior to islet transplant. Doses 2 to 5 will be 1 mg/kg will be given every 2 weeks starting on day 14 after the subsequent transplant.

If a third transplant is deemed necessary and performed between 30 and 70 days after the second transplant, no additional doses of daclizumab will be given.

If a third islet transplant is deemed necessary and performed more than 70 days after the second transplant (see Section 7.5 for indications for subsequent transplants), all five doses of daclizumab will be repeated.

# 5.2.2.1.2 Basiliximab (Simulect®)

Two I.V. doses of basiliximab will be given with the first and second (if necessary) transplants. The first dose will be 20 mg and will be given within two hours prior to islet transplant on the day of islet transplantation. The second dose will be given on Day 4 after the transplant.

If a third transplant is deemed necessary and performed between 30 and 70 days after the second transplant, no additional doses of basiliximab will be given.

If a third islet transplant is deemed necessary and performed more than 70 days after the second transplant (see Section 7.5.1 for indications for subsequent transplants), both doses of basiliximab will be repeated.

#### 5.3 Concomitant Medications

#### 5.3.1 Antibacterial, Antifungal, and Antiviral Prophylaxis

Broad spectrum antimicrobial prophylaxis should be administered preoperatively according to site-specific standards, or as the Transplant Infectious Disease. consultant recommends.

# 5.3.1.1 Trimethoprim/Sulfamethoxazole (Septra SS®/Bactrim®)

Trimethoprim / sulfamethoxazole will be administered at a dose of 80 mg/400 mg PO QD starting on Day +1 for the duration of study follow-up. In the event that a subject is unable to take trimethoprim/sulfamethoxazole, he/she will be treated on a case-by-case basis as is medically indicated.

# 5.3.1.2 Clotrimazole (Mycelex Troche®)

Clotrimazole will be administered as 1 troche PO QID starting on Day –2 relative to transplant, to be continued for 3 months after transplantation. Alternatively, antifungal prophylaxis per standard practice at each site may be administered instead of clotrimazole.

# 5.3.1.3 Valganciclovir (Valcyte®)

Valganciclovir will be administered starting on Day -2 at a dose of 450 mg PO QD, increasing to 900 mg QD by day 12 and continuing for 14 weeks post-transplant (irrespective of CMV status of donor or recipient).

## 5.3.2 Anticoagulation Prophylaxis/Hematological Agents

#### **5.3.2.1** Heparin

Heparin will be administered at a dose of 70 U/kg body weight of recipient, divided equally among the islet bags, given with islet infusion, followed by 3 U/kg/hr IV for the next 4 hrs. From the 5th through the 48th hr post-transplant, heparin will be titrated to achieve and maintain partial thromboplastin time (PTT) between 50-60 seconds. If the site does not use PTT to titrate heparin, a comparable site-specific method and value should be used.

# 5.3.2.2 Enoxaparin (Lovenox®)

Enoxaparin will be administered at a dose of 30 mg SC BID through day 7 post-islet transplant, with the first dose given 48 hours after the transplant procedure (when heparin is discontinued).

### **5.3.2.3** Pentoxifylline

Pentoxifylline will be administered at a dose of 400 mg slow release TID beginning 2 days prior to transplant (Day -2) and continuing for 7 days post-transplant (Day 7).

### **5.3.2.4** Aspirin

Enteric coated aspirin will be administered at a dose of 81 mg PO qPM starting 24 hrs post-transplant, and continued as medically indicated.

## 5.3.3 Insulin Therapy

Glucose levels will be targeted to 80-120 mg/dL. Insulin (*e.g.* Regular, Lispro, NPH, Glargine) will be administered as needed to maintain glucose levels in the target range. The subject will test BG five times per day (AM fasting, before lunch, 2 hours after lunch, before supper, and at bedtime). The subject's daily BG levels will be reviewed by a study nurse and/or one of the investigators three times per week during the first two weeks after discharge, and then weekly during the next month. Exogenous insulin will be withdrawn or adjusted as needed. Patients able to maintain fasting BG levels below 140 mg/dL and 2-hour post-prandial levels below 180 mg/dL after insulin discontinuation will be considered insulin independent.

#### 5.3.4 Other Standard Therapies

Anti-hypertensive, anti-hyperlipidemia and other approved therapies for pre-existing and new medical conditions will be provided per standard of care. Pre- and post-islet transplant procedure drug regimens (*e.g.*, pre-transplant sedation and anesthetic) will be given per standard of care.

#### 5.4 Rescue Medications

Rescue therapy will not be initiated in this protocol to treat suspected rejection. Immunologic surveillance methods that would allow diagnosis of islet allograft rejection early enough for timely intervention have yet to be identified and validated.

#### 5.5 Prohibited Medications

Prohibited medications for this protocol, except as specifically indicated in this protocol include:

- steroid medication (save topicals and prednisone at a dose of ≤5 mg daily, or an equivalent dose of hydrocortisone, for physiological replacement only)
- any medications in the macrolide antibiotic class

- other investigational products
- other immunosuppressive therapies
- immunomodulatory agents
- other anti-diabetic agents
- Dapsone

## 5.6 Assessment of Compliance with Study Treatment

Assessment of subject compliance will be determined by the completion of scheduled study visits and required documentation that the specific subject is responsible for (*e.g.*, Blood Glucose Logs, AE and Insulin Use recording) as well as their willingness to comply with the recommendations of the study investigators. Glucometers will be downloaded for verification of the blood glucose values recorded in the subjects' logs. Any aberration of trough levels of immunosuppressive agents that could indicate nonadherence, lack of compliance that poses a significant clinical risk and or derangement of protocol data collection will be documented. Please refer to Section 5.7.2 for a description of possible indications for premature discontinuation of study treatment.

Compliance with the maintenance immunosuppression medications used in this protocol (tacrolimus and rapamycin) will be assessed by regular monitoring of their plasma trough concentrations (please refer to section 6).

## 5.7 Modification or Discontinuation of Study Treatment

## 5.7.1 Modification of Consensus Immunosuppression Regimen

Should an islet product become unsuitable for transplantation subsequent to recipient randomization and treatment with induction immunosuppression, the subject will remain on maintenance therapy for 2 weeks. This will provide sufficient time for organ procurement, islet isolation, and infusion of an islet product without any additional induction treatment of the recipient. An emergency request will be placed through UNOS to ensure that the next available pancreas for islet transplantation is directed to the selected manufacturing site. Should an islet product not be available during this 2 week period, the subject will continue maintenance immunosuppression, but induction with a monoclonal antibody IL-2 receptor blocker will be administered at the time of the islet transplant. If an adequate islet product does not become available within a 30 day period, immunosuppression will be discontinued, as per site specific standards, and the case will be considered a treatment failure.

In the event that protocol-regulated concomitant medications are not tolerated, the subject will continue taking the immunosuppressive therapy in order to protect the islet graft. In the event that the immunosuppression regimen is not tolerated, the Site Principal Investigator (PI) may elect to prescribe an alternative immunosuppression regimen. The intent would be for the alternative regimen to be temporary in nature where possible. Any non-protocol directed study

treatment modification that the site PI determines is necessary should be reported as a protocol deviation.

#### 5.7.1.1 Rabbit Anti-Thymocyte Globulin-Induced Anaphylaxis

In rare instances, anaphylaxis has been reported with Thymoglobulin® use. In such cases, the infusion should be terminated immediately. Medical personnel should be available to treat subjects who experience anaphylaxis. Emergency treatment such as 0.3 mL to 0.5 mL aqueous epinephrine (1:1000 dilution) subcutaneously and other resuscitative measures including oxygen, IV fluids, antihistamines, corticosteroids, pressor amines, and airway management, as clinically indicated, should be provided. Thymoglobulin® or other rabbit immunoglobulins should not be administered again for such subjects.

# 5.7.1.2 Rabbit Anti-Thymocyte Globulin and Rituximab-Induced Cytokine Release

Thymoglobulin® and rituximab infusions may cause cytokine release-related fever and chills. To minimize these, the first dose should be infused over a minimum of 6 hours into a high-flow vein. Also, premedication with corticosteroids, pentoxifylline, acetaminophen, and/or an antihistamine will be provided in order to minimize the reaction incidence and/or intensity. At any sign of the above reaction, slowing the infusion rate by 50% will also occur.

# 5.7.1.3 Neutropenia

Neutropenia is an expected consequence of the administration of several medications in this protocol. Subject safety is of utmost importance. Clinical treatment decisions take precedence over recommended guidelines.

If a subject's absolute neutrophil count is less than 1000 cells/ $\mu L$  and the patient is afebrile, then the following will be done:

- Reduce rabbit ATG by 50%.
- Reduce the prophylactic use of valganciclovir from 900 grams per day to 450 mg per day or hold valganciclovir.
- Reduce trimethoprim/sulfamethoxazole to 80/400 mg on Monday, Wednesday, and Friday or hold trimethoprim/sulfamethoxazole.
- Review and obtain current sirolimus trough levels and consider dosage adjustment if trough level are >12ng/mL
- If subject is using mycophenolate mofetil or mycophenolate sodium in lieu of sirolimus or tacrolimus consider dose reduction.
- Consider administration of G-CSF.
- Monitor temperature BID.

• Follow-up within 48-72 hours to obtain: repeat complete blood count (CBC) with differential, patient symptoms, and measured temperatures.

# If a subject's absolute neutrophil count is less than 1000 cells/ $\mu$ L and the subject is febrile, then the following will be done:

- Obtain Infectious Disease Consult.
- Hold rabbit ATG.
- Hold valganciclovir and trimethoprim/sulfamethoxazole.
- Review and obtain current sirolimus trough levels and consider dosage adjustment if trough level are >12ng/mL.
- If subject is using mycophenolate mofetil or mycophenolate sodium in lieu of sirolimus or tacrolimus consider dose reduction.
- Administer G-CSF.
- Monitor temperature BID.
- Follow-up within 48-72 hours to obtain: repeat CBC with differential, subject symptoms, and measured temperatures.

# If a subject's absolute neutrophil count is measured as less than 500 cells/ $\mu L$ and the subject is afebrile, then the following will be done:

- Hold rabbit ATG.
- Hold administration of trimethoprim/sulfamethoxazole and/or valganciclovir.
- Review and obtain current sirolimus trough levels and hold dose if trough level are >12ng/mL.
- If subject is using mycophenolate mofetil or mycophenolate sodium in lieu of sirolimus or tacrolimus consider holding dose.
- Obtain CMV antigenemia or PCR for CMV.
- Consider fluoroquinolones in afebrile patients.
- Consider clotrimazole.
- Administer G-CSF.
- Monitor temperature BID.
- Follow up within 24 hours to obtain repeat CBC, subject symptoms, and measured temperatures.

# If a subject's absolute neutrophil count is measured as less than 500 cells/ $\mu L$ and the subject is febrile, then the following will be done:

• The subject will be hospitalized under neutropenic precautions and Infectious Disease/Hematology consult will be obtained.

- Hold rabbit ATG.
- Hold administration of trimethoprim/sulfamethoxazole and/or valganciclovir.
- Review and obtain current sirolimus trough levels and hold dose if trough level are >12ng/mL.
- If subject is using mycophenolate mofetil or mycophenolate sodium in lieu of sirolimus, or tacrolimus consider holding dose.
- Obtain CMV antigenemia or PCR for CMV.
- Administer G-CSF.

## 5.7.1.4 Thrombocytopenia

If the subject is found to have a platelet count (PLT) of  $<50 \times 10^9$ /L, ATG will be withheld until PLT  $>50 \times 10^9$ /L, then resume at a 50% reduced dose. If the PLT is  $<50 \times 10^9$ /L, sirolimus will be withheld for 24 hours, then resumed at a 50% reduced dose. If PLT fails to return to  $>50 \times 10^9$ /L within one week, sirolimus is to be withheld until PLT  $>50 \times 10^9$ /L, after which sirolimus is resumed at 50% of the dose that preceded the drop in PLT to  $<50 \times 10^9$ /L. If the PLT is between 50 and 75 x  $10^9$ /L, reduce ATG dose by 50% until PLT is  $>75 \times 10^9$ /L.

# 5.7.1.5 Nephrotoxicity:

A sustained 33% increase in serum creatinine or a 33% decrease in GFR warrants a prompt referral to a nephrologist for evaluation. If it is determined that the decrease in renal function is attributable to CNI immunosuppressive therapy, the treating physician should chose ONE of the therapeutic alternatives shown in the following table:

Table 2: Response to nephrotoxicity

Allowable therapeutic responses to CNI-induced nephrotoxocity	Rationale
Discontinue sirolimus, and replace it with mycophenelate mofetil or mycophenolate sodium.	The nephrotoxic effect of CNIs is increased by concomitant administration of sirolimus 123, 157.
If the trough sirolimus level is maintained at >10 ng/mL without adverse effects, discontinue the CNI and replace it with mycophenolate mofetil or mycophenolate sodium.	CNI should be discontinued only if the subject can tolerate a trough level of sirolimus that will result in adequate immunosuppression.
Decrease the target CNI trough level by 25%.	CNI toxicity is dose-related.

A repeat assessment of GFR should be performed 3 months after the change in immunosuppression.

Anti-hypertensives, anti-hyperlipidemics and other approved therapies for pre-existing and new medical conditions will be provided per standard of care.

# 5.7.2 Premature Discontinuation of Study Treatment (Transition to "Off-Protocol" Treatment)

Study treatment may be prematurely discontinued for any subject for any of the following reasons:

- 1. The subject is unwilling or unable to comply with the protocol.
- 2. The investigator believes that the study treatment is no longer in the best interest of the subject.
- 3. Graft Failure: Islet allograft failure will be defined as absence of insulin production by transplanted islets, as evidenced by absence of c-peptide. This will be determined by (1) undetectable c-peptide on random testing, followed by (2) undetectable c-peptide at baseline, and at 60 and 90 minutes after MMTT. C-peptide levels obtained in the course of the MMTT will be run at the core lab in Seattle, WA. All study treatment will be tapered and discontinued, at the discretion of the site Principal Investigator, when it is determined that graft failure has occurred.
- 4. An unexpected related SAE. The agent(s) to which the event is attributed will be discontinued.

Subjects who prematurely discontinue study treatment will remain in the study until normal termination, for the purpose of monitoring safety and efficacy parameters and will enter the reduced follow-up schedule outlined in Appendix 2. Data from these subjects will be used in the intent-to-treat analysis. These subjects are permitted to simultaneously enroll in a CIT or site-specific graft failure follow-up protocol, if available.

## 6. CRITERIA FOR PREMATURE TERMINATION OF THE STUDY

# 6.1 Subject Withdrawal Criteria

Subjects may be prematurely terminated from study for the following reasons:

- 1. The subject elects to withdraw consent from all future study activities, including follow-up.
- 2. The subject is "lost to follow-up" (*i.e.*, no further follow-up is possible because attempts to reestablish contact with the subject have failed).
- 3. The subject dies.

Subjects who prematurely terminate from this study will not be replaced. Data from such subjects obtained before withdrawal of consent or before being lost to follow up will be used in the intent-to-treat analysis. If a subject with functioning transplanted islets chooses to withdraw from the protocol, s/he must be informed of their risk for losing his/her islet graft and becoming sensitized if s/he chooses to discontinue immunosuppressive therapy and return to his/her original method of insulin management.

# 6.2 Study Stopping Rules

# 6.2.1 Protocol Suspension and Review

Study enrollment at all participating clinical sites will be suspended pending expedited review of all pertinent data by the institutional review board (IRB), the National Institute of Allergy and Infection Disease (NIAID), the National Institute of Diabetes and Digestive and Kidney Diseases (NIDDK), and the NIDDK Data Safety Monitoring Board (DSMB), if any one of the following occurs:

- 1. The Medical Monitor finds any unexpected fatal or life-threatening AE possibly related to the use of the test therapy;
- 2. Primary non-function occurs in 3 or more consecutive subjects at 2 or more participating clinical sites. Primary non-function (PNF) is defined by undetectable cpeptide levels (1-3 hours post-prandial) between 3-7 days post transplant;
- 3. There are 6 consecutive study subjects with a c-peptide less than 0.3 ng/mL (on random testing, at baseline and 1-3 hrs post MMTT) at 75 days post-transplant;
- 4. Any event(s) which in the opinion of the Medical Monitor or Protocol Chair indicates the need for DSMB review; or
- 5. The DSMB recommends termination of protocol enrollment and further transplants on a study-wide basis based on a review of the data and finding evidence that such action is necessary. Statistical guidelines for terminating the study based on monitoring guidelines are provided in section 10.

After the protocol is placed on hold, no additional transplants within the trial will be performed at any participating clinical site until the CIT Steering Committee and DSMB meet either in person or by conference call to review in depth the results and circumstances surrounding the islet functional failure or SAE to determine whether the trial enrollment of new subjects and conduct of additional transplants could be safely resumed.

# 6.2.2 Site Suspension and Review

Study enrollment and initial islet transplants will be suspended (placed on hold) at a participating clinical site, pending expedited review of all pertinent data by the IRB, the NIAID, the NIDDK, and the NIDDK DSMB, if any one of the following occurs:

- 1. Any possibly study-related grade 5 AE; or
- 2. Two SAEs related to the islet transplant procedure (*e.g.* bleeding, thrombosis, gall bladder injury); or
- 3. Two consecutive primary non-functioning transplants defined by undetectable c-peptide levels (1-3 hours postprandial) between 3-7 days post transplant.

After any site is placed on hold, no additional transplants will be performed at that site until the CIT Steering Committee and DSMB meet either in person or by conference call to review in depth the results and circumstances surrounding the islet functional failure or SAE to determine whether the trial enrollment of new subjects and conduct of additional transplants could be safely resumed at that site, or whether there could be implications for the continuation of the entire proposed pilot protocol also at other affiliated sites testing the same protocol.

In all cases of PNF, subjects will be asked to temporarily continue immunosuppression to decrease the risk of sensitization that could increase the risk of poor outcome should future transplants occur. A tapering schedule will be applied until immunosuppressants are completely discontinued.

## 7. STUDY PROCEDURES

#### 7.1 Enrollment

This research study will be explained in lay terms to each potential research subject. The potential subject will sign an informed consent form before undergoing any screening study procedures. Subjects who are deemed eligible for the study (see sections 4.0) will be enrolled and assigned a unique subject number.

Once an Islet Transplant has been provided, the patient becomes a part of the intention-to-treat population. All transplanted subjects will be included in the primary analysis.

This will be an open-label, prospective, single-arm, single-center study. The addition of rituximab to the CIT-07 strategy with elimination of the CNI tacrolimus will be evaluated. All islets will be processed at the University of Pennsylvania where all subjects will be recruited.

Unless the study is terminated early, recruitment will continue until the maximum sample size is reached, at which point recruitment will be terminated. It is anticipated that accrual of subjects will take 24 months.

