#### 7.4 Randomization

Once a compatible islet prep becomes available, subject eligibility will be re-confirmed. Eligible subjects will be randomized on Day -2 relative to transplant, between CIT-05 and CIT-07. Subjects randomized will receive immunosuppressive therapy beginning on Day -2 (see Section 5 for full description of Study Treatment Regimen). Subjects will receive the initial islet transplant on Day 0 and will continue the immunosuppression regimen detailed in Section 5.

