### 10. STATISTICAL CONSIDERATIONS AND ANALYTICAL PLAN

## 10.1 Statistical Analyses

The goal of this study is to provide strong scientific evidence that the rate of favorable outcome in transplanted subjects is high enough to justify the risks of the procedure and the immunosuppression. All efficacy analyses will be based on the intention-to-treat principle. Once a subject has been transplanted s/he will be included in the final analysis. All transplanted subjects will also be included in the safety analysis. There will be planned interim analyses for safety and efficacy at the direction of the DSMB. Details of all statistical analyses will be given in the formal statistical analysis plan (SAP).

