# 10.2 Study Endpoint Assessment

# 10.2.1 Primary Endpoint

The primary objective of the analysis is to estimate the rate of insulin independence at 75 days after the first Islet Transplant among those in the study. The primary endpoint is insulin independence (yes/no) at day 75 after Islet Transplant as defined in section 3.1. The primary analysis will compute an exact binomial estimate and a 95% confidence interval for the true rate.

The primary endpoint should be available for all randomized subjects. An exception will be if a death occurs or if the subject withdraws consent to be followed, in these cases the endpoint will be classified as failure to achieve insulin independence. Should the endpoint not be evaluated for a particular individual for other reasons, a failure will be imputed unless an evaluation is done at a time longer than 75 days after transplant and before an additional islet transplant, in which case that later value will be imputed. All imputations will be reported with the primary analysis.

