				P	RCH	IVED	SAMI	PLES								
Serum		Х								X			Х	X	Χ	Х
PBMC & Plasma		Х								Х			Х	Х	X	Χ
RNA		Х								Х			Х	Χ	Χ	Х

 WL = Waiting List. BL = Baseline. Repeat assessments as indicated (i.e. yrly, q3mo), while subject is on the waiting list. All one-time WL/BL assessments should be completed on Day -2 whenever possible, but always prior to start of immunosuppression. For repeat WL/BL assessments, results from test done closest to the start of immunosuppression will be used as the baseline value.

<sup>2 Day 0 = the day of transplant. This SOE applies to the  $1^{st}$ ,  $2^{nd}$ , and  $3^{rd}$  transplant as applicable. The SOE is restarted at Day 0 for each subsequent transplant.

<sup>3 Informed Consent #1 includes information on CIT-07 and CIT-05 protocols.

<sup>4 Informed Consent #2 includes information specific to CIT-05. IC #2 must be signed immediately after randomization.

<sup>5 FOBT (take-home multiple sample method) or FIT w/in last yr, flexible sigmoidoscopy w/in last 5 yrs, double-contrast barium enema w/in last 5 yrs, colonoscopy w/in last 10 yrs. All positive tests should be followed up with colonoscopy.

<sup>6Retinopathy eval includes fundoscopic pictures for WL/BL assessments and Y1. Screening retinopathy evaluation should be done per site-specific standards.

<sup>7 Chemistry includes: Sodium, albumin, magnesium, chloride, potassium, alk phosphatase, total bilirubin, CO2, creatinine, ALT (SGPT), BUN, gamma GT, glucose, AST (SGOT), calcium, phosphorus.

<sup>8 Complete pregnancy test within 72 hours prior to randomization.

<sup>9 Serology includes: HBc Ab, HBs Ab, HBs Ag, HCV Ab, HIV, and HTLV-I/II. Do not repeat Hepatitis B tests if HBs Ab was previously positive.

<sup>10 Repeat only if previous test was negative.

<sup>11 Repeat for subsequent transplant(s).

<sup>12 Sample used for crossmatch may be obtained up to 60 days prior to the start of immunosuppression, as long as there is no evidence of infections or transfusions since the time the sample was drawn. Repeat crossmatch for subsequent transplants.

<sup>13 C-peptide should be done locally and drawn fasting, and twice between 1-3 hours post-prandial on Day 3 and Day 7 post-transplant.

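### Sections 7.1 and 10.1 start the intention-to-treat and safety sets at transplantation, in conflict with sections 5.7.1 and 10.2.1, so the primary denominator is not uniquely fixed and the safety set as worded does not cover subjects induced but never transplanted

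*Protocol*

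**What the plan says.** **Entry at transplantation.** Section 7.1 (Enrollment) states: "Once an Islet Transplant has been provided, the patient becomes a part of the intention-to-treat population". It continues: "All transplanted subjects will be included in the primary analysis". Section 10.1 (Statistical Analyses) commits all efficacy analyses to the intention-to-treat principle and then says: "Once a subject has been transplanted s/he will be included in the final analysis". For safety it says: "All transplanted subjects will also be included in the safety analysis".

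**Entry at randomization.** Section 7.4 places the randomization between CIT-05 and CIT-07 on Day -2, with transplant on Day 0, and adds: "Subjects randomized will receive immunosuppressive therapy beginning on Day -2". Section 10.2.1 says: "The primary endpoint should be available for all randomized subjects". It scores death and withdrawal of consent to be followed as failures. It also imputes failure where the endpoint is not evaluated for another reason, unless a later evaluation exists before any further transplant.

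**The case between the two.** Section 5.7.1 covers an islet product that becomes unsuitable after randomization and induction. If no adequate product is found within 30 days, "immunosuppression will be discontinued, as per site specific standards, and the case will be considered a treatment failure".

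**Safety data.** Section 8.2.1 collects most adverse events from randomization onward; procedure-related and hypoglycemic events are collected from enrollment consent.

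**The concern.** A subject can be randomized and induced yet never receive islets. The protocol expects this: under section 7.5 the islets stay in culture for about 48 hours after induction begins and must meet release criteria again on Day 0. Section 5.7.1 calls the no-product case a failure, but sections 7.1 and 10.1 contain no rule that brings the subject into an analysis set. Section 10.2.1 would count the subject.

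Three things depend on which text is followed:

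- **The primary rate.** Leaving out a designated failure raises it.
- **The comparison with CIT-07** (section 10.2.2) and the early-stopping boundary (section 10.5). The stated purpose of randomization is balance and objective selection. Restricting both groups to transplanted subjects conditions the comparison on something that happens after allocation, in an open-label study.
- **The safety denominators.** Section 5.2.1.1 gives the first rituximab dose between Day -2 and Day -1 and notes that infusion reactions mostly occur with that dose. This exposure comes before entry to the safety set.

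**Working it through.** **Step 1: follow one subject through the text.** Take a subject randomized to CIT-05 on Day -2 and induced, whose product fails on Day 0 and for whom no other product is found within 30 days.

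| Section | Status of this subject |
|---|---|
| 5.7.1 | Treatment failure |
| 7.1 | Never enters the intention-to-treat population; not among those listed for the primary analysis |
| 10.1, efficacy | Not among those listed for the final analysis |
| 10.1, safety | Not among those listed for the safety analysis |
| 10.2.1 | Randomized, so the endpoint is expected; not evaluated, so failure is imputed |
| 8.2.1 | Adverse events collected from randomization |

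The endpoint is timed from the first transplant, so this subject has no day 75. Only the imputation rule in 10.2.1 can produce a score. Sections 5.7.1 and 10.2.1 give a failure in the denominator; 7.1 and 10.1 do not. For safety, no section offsets the wording in 10.1.

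**Step 2: reproduce the plan's own figure.** Section 10.4 gives n = 12 and, for 6 responders, 50% with an exact 95% interval of 0.21 to 0.79. The exact (Clopper-Pearson) limits for x responders out of n are:

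- lower = 0.025 quantile of Beta(x, n − x + 1)
- upper = 0.975 quantile of Beta(x + 1, n − x)

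For x = 6 and n = 12 these give 0.211 and 0.789, which matches.

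**Step 3: add untransplanted failures.** Let m be the number randomized and induced but never transplanted. The documents do not give m, so 1 and 2 are assumptions, as is adding them on top of 12 transplanted subjects. The rate becomes x/(12 + m), which is x/12 multiplied by 12/(12 + m): a factor of 12/13 = 0.923 for m = 1 and 12/14 = 0.857 for m = 2.

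| Responders | m = 0 | m = 1 | m = 2 |
|---|---|---|---|
| 4 | 33.3% (0.10-0.65) | 30.8% (0.09-0.61) | 28.6% (0.08-0.58) |
| 5 | 41.7% (0.15-0.72) | 38.5% (0.14-0.68) | 35.7% (0.13-0.65) |
| 6 | 50.0% (0.21-0.79) | 46.2% (0.19-0.75) | 42.9% (0.18-0.71) |
| 7 | 58.3% (0.28-0.85) | 53.8% (0.25-0.81) | 50.0% (0.23-0.77) |

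One omitted failure is worth 41.7 − 38.5 = 3.2 points at 5 responders and 50.0 − 46.2 = 3.8 points at 6. Only the 5-responder row crosses the 40% mark named in the Study Design section.

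**Step 4: the other way of counting.** Section 10.4 does not say whether the 12 are counted at randomization or at transplant. If 12 are randomized and one is not transplanted, 4/11 = 36% compares with 4/12 = 33%, and 5/11 = 45% with 5/12 = 42%, so neither pair crosses 40%. If two are not transplanted, 4/10 = 40% compares with 4/12 = 33%.

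**The case against.** The strongest reply is that the primary endpoint section already gives the sensible answer. Section 10.2.1 refers to all randomized subjects and imputes failure. Sections 7.1 and 10.1 say that transplanted subjects will be included; they do not say that nobody else will be. Section 6.1 also puts data from prematurely terminated subjects into the intention-to-treat analysis. A reader might infer that untransplanted subjects are definitely dropped from the primary analysis. The documents do not support that; they support an unresolved conflict. The conflict still stands, because 7.1 defines entry to the population by transplant and an SAP cannot follow both texts.

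Second, section 2.1 asks for the proportion among subjects treated with the regimen. For a 12-subject pilot, a treated set is a recognised choice. This stands as an argument against automatically scoring people who were never dosed as failures in the primary analysis. It does not help with subjects who were dosed and whom 5.7.1 calls failures.

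Third, a reader might infer that a single such subject decides the 40% benchmark. With one subject added to 12 transplanted, that happens only at exactly 5 responders. The 40% figure is also not a decision rule: at that rate the treatment may be considered for further study. The intervals for 5/12 and 5/13 nearly coincide.

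Fourth, because Appendix 1 says "IC #2 must be signed immediately after randomization", a reader might infer that subjects first learn of the experimental regimen after allocation. Footnote 3 of the same appendix says the first consent already covers both protocols, so consent timing forms no part of this point.

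Fifth, adverse events before transplant are monitored. Section 8.2.3 requires specified serious outcomes for all randomized subjects, and section 8.3.3.4 sends listings of all events to the DSMB. What remains is the population for the planned safety analysis.

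**Conclusion.** The point holds as an internal contradiction with a modest numerical effect. The protocol gives two readings of the primary denominator and labels as intention-to-treat a set that begins after randomization and after treatment has started. For safety the gap is plainer: as 10.1 is worded, subjects exposed to Thymoglobulin and rituximab but never transplanted lie outside the safety set, although their events are collected.

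With 12 transplanted and one or two more induced but untransplanted, the estimate at 6 responders falls from 50% to 46% or 43%. The count of one or two is an assumption; if nobody goes untransplanted, no figure changes. The treatment-failure label in 5.7.1 covers only the case of no product within 30 days. Subjects left untransplanted for other reasons are reached only by the general imputation rule in 10.2.1.

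**What to change.** Reconcile sections 5.7.1, 7.1, 10.1 and 10.2.1 so that they state one set of definitions:

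- **Primary efficacy set:** every subject randomized to CIT-05 who started study immunosuppression. Those never transplanted, for whatever reason, are scored as not insulin independent.
- **Randomized but never dosed:** report each such subject and include them in a sensitivity analysis by randomized allocation.
- **Safety set:** all subjects who received any dose of study immunosuppression.
- **CIT-07 comparison group:** the same definitions, including for the interim comparisons in section 10.5.
- **Transplanted-only analysis:** keep it as a sensitivity analysis, labelled modified intention-to-treat.

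Section 10.4 should also say at which point the 12 subjects are counted.

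The cost is a few sentences of wording and no new data collection, since adverse events are already collected from randomization. The price is that the primary rate may be slightly less favourable.
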